Statistical Analysis Plan

Produced during publication of data

[name], [name], [name], [name], [name]; Development and Preliminary Evaluation of a Smartphone App for Measuring Eye Alignment. *Trans. Vis. Sci. Tech.* 2019;8(1):19.

August 1, 2019

Aim 1: Simulated Strabismus

The Hirschberg ratio (HR) for each subject was determined using data from all 13 fixation points by plotting the app measurement against the known angular deviation for each fixation point, and determining best fit of this scatter plot using linear regression. The slope of this function represents the individual's HR and the *y*-intercept is the individual's angle κ (the angle between the visual and optical axes, represented as κ).^{18,19} We measured the within-subject test–retest repeatability of the app in estimating the HR and κ using a Bland-Altman²⁰ plot to compute 95% confidence interval (CI) of the difference between two trials. Furthermore, we tested the accuracy of using a population average value of the HR by comparing the absolute gaze angles estimated by the app measurements and the true deviation of the fixation targets (via regression analysis using MATLAB; Mathworks, Natick, MA). The HR used for a subject was the average HR of the rest of the subjects.

Aim 2: Strabismus

Linear regression analysis was used to compare the app measurements of strabismus angle with cover test with prism neutralization CTPN measurements. Since the CTPN measurements were done at near fixation to facilitate direct comparison with the app measurements, corrections were made to the recorded CTPN values during data processing to account for the finite distance between the prism and center of rotation of the eye.²² We arrived at a value of the distance between prism and center of rotation of eye by assuming a population average value of 24 mm for axial length²³ and a back vertex distance of 10 mm.

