## Secondary outcome:

1) Accuracy of the app quantified by calculating the mean difference between the app and simulated or measured strabismus.

2) Test-retest repeatability

3) Robustness measure: calculation of the percentage of capture failures (capture failures/ total number of attempted image captures)

4) Analysis of the effect of different factors (i.e. age, iris color, refractive error) on the accuracy.

5) Success rate of tele-strabismus consult and perceived value (captured in a perceived value survey).

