#### **Ground truth study:**

The subjects will sequentially fixate on the targets of known eccentricity placed on the rear surface of the smartphone along the horizontal direction with their head stabilized in a chin forehead rest (Fig. 3). The app does not need to be used in this manner in actual practice; however, for the purpose of establishing the true deviation values for the fixation targets, such a controlled setup was necessary. The test setup covered an angular range of  $\pm 13$  degree (approximately  $\pm 23D$  with respect to a central fixation corresponding to camera lens).

Figure 3. Experimental setup to measure the accuracy of the app in Study 1. Subjects without strabismus fixated on 13 targets on the rear side of a smartphone placed at a distance of 30 cm with their head resting on a chin–head rest. Twelve of the 13 fixation targets were a black cross on a white background. The center target was the smartphone camera. With the known distances, true eye deviation magnitudes with respect to the central fixation point were computed (angular range covered by the fixation targets was 6138 or 623D) and compared to measurements with the app.

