#### **Clinical study:**

In a second study, dissociated phoria measurements with the app will be compared to the Modified Thorington (MT) test. Subjects will rest their head in a chin-head rest and the phone will be mounted 40 cm from the eyes. A 20/30 size letter attached below the phone camera lens served as a fixation point and controlled accommodation. The eyes will be alternately covered and then uncovered by an examiner with an occluder while the subject maintained the fixation. The app generated auditory tones to guide the examiner when to change the cover from one eye to the other. A higher-pitched tone was a cue to stop alternate cover and to uncover both eyes. The app recorded for 2 seconds after the final higher-pitched tone, resulting in 30 recorded frames. The app displayed the recorded frames and the user swiped through the frames to find and select the first frame after uncovering the eyes, which then was processed by the app to output the measurement value. Each subject was tested three times with the app in quick succession. Phoria also was measured using an MT near card (at 40 cm).

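### In the Aim 1 accuracy regression, a pooled slope near 1 is built in by the leave-one-out HR and cannot show that a population HR suits an individual; handling of repeated points within a subject is not stated

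*SAP*

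**What the plan says.** SAP, Aim 1, has three steps.

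- HR (slope) and kappa (intercept) are fitted for each subject "using data from all 13 fixation points".
- A Bland-Altman plot of HR and kappa is used to "compute 95% confidence interval (CI) of the difference between two trials".
- The accuracy of a population-average HR is tested by comparing app-estimated gaze angles with true target angles "via regression analysis using MATLAB". For this step, "The HR used for a subject was the average HR of the rest of the subjects".

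For the third step the SAP does not say whether all subjects go into one line, whether both trials enter, whether kappa is removed, or how repeated points within a subject are handled. It states no standard error, interval or test for this regression, and no limits of agreement for app minus true angle.

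The protocol (Ground truth study) describes the design: "Subjects without strabismus fixated on 13 targets on the rear side of a smartphone", over ±13 degrees (about ±23 D). Its Secondary outcome 1 is "Accuracy of the app quantified by calculating the mean difference between the app and simulated or measured strabismus". The SAP does not take up that mean difference.

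**The concern.** The third step asks whether one HR can serve for everybody. The quantity that answers it is how far a single person's slope departs from 1 when other people's HR is applied. A pooled slope averages those departures, and the leave-one-out scaling makes them cancel almost exactly. A reader shown a slope of 1.00 would take it as support for the population HR, although the analysis would give that value whether subjects differed a little or a lot.

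A second, smaller matter is clustering. The SAP itself treats HR and kappa as properties of the individual, so points from one subject share both. An interval for the protocol's mean difference that counted every reading as independent could be much too narrow.

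**Working it through.** **Inputs from the documents.** 13 targets per subject; range ±13 degrees; two trials, named only for repeatability; leave-one-out mean HR. The stated conversion checks: 100 × tan(13°) = 23.1 D. There is no stated slope, standard error or sample size for this regression to reproduce.

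**Assumptions, not in the documents.** Equally spaced targets; 10 or 25 subjects; between-subject HR CV 5-10%; reading noise SD 1 degree; kappa SD 0 or 1 degree; both trials pooled, so 26 points per subject; HR taken from the same readings; app estimate as the response (the SAP's HR fit has the app reading on that axis). Mean squared target angle: 14 × (26/12)² = 65.72.

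**1. Pooled slope.** Let b_i be subject i's fitted HR and m_i the mean of the others. Subject i's slope after scaling is s_i = b_i / m_i; kappa moves only the intercept. With the same targets for everyone, the pooled least-squares slope is the plain average of the s_i. Write b_i = b̄(1 + d_i) with the d_i summing to zero. Then m_i = b̄(1 − d_i/(n − 1)), and the average of s_i is about 1 + CV²/(n − 1), where CV is that of the fitted HRs. Slope noise within a subject is 1/√(26 × 65.72) = 0.024.

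- n = 10, CV 10%: fitted CV = √(0.10² + 0.024²) = 0.103; slope = 1 + 0.103²/9 = 1.001.
- n = 25, CV 5%: fitted CV = √(0.05² + 0.024²) = 0.055; slope = 1 + 0.055²/24 = 1.000.

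Simulation (3,000 runs per scenario) gives 1.000-1.001, with sampling SD at most 0.0006.

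**2. Individual slopes.** The SD of s_i is about the fitted CV × n/(n − 1): 0.055 × 25/24 = 0.06 and 0.103 × 10/9 = 0.11. Simulation gives 0.06-0.11.

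**3. Error at the largest angle.** A subject 2 SD from the mean HR is off by 13 × 2 × 0.05 = 1.3 degrees at CV 5%, and 13 × 2 × 0.10 = 2.6 degrees at CV 10%. As a yardstick, the protocol (Background) says the app can measure differences of 1.6 degrees (2.8 D).

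**4. Slope against error** (20 subjects, kappa removed per subject so that only HR spread and noise remain):

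| HR CV | Pooled slope | 95th percentile of absolute error |
|---|---|---|
| 0% | 1.000 | 1.9 degrees |
| 5% | 1.000 | 2.1 degrees |
| 10% | 1.001 | 2.5 degrees |
| 15% | 1.001 | 3.2 degrees |

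The error grows and the slope does not move.

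**5. Standard error of the mean difference or intercept.** The two coincide to a close approximation because the targets are symmetric and the slope is about 1. Per subject, the true variance is κ² + σ²/26. The independent-points version is (κ² + σ² + CV² × 65.72)/26.

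- Kappa SD 1, CV 5%: √[1.038 / (2.164/26)] = 3.5 times too small.
- Kappa SD 1, CV 10%: √[1.038 / (2.657/26)] = 3.2 times too small.
- One trial only, kappa SD 1, CV 5-10%: √[1.077 / (2.164/13)] = 2.5 and √[1.077 / (2.657/13)] = 2.3.
- Kappa SD 0, both trials, CV 5-10%: √(1/1.164) = 0.93 and √(1/1.657) = 0.78, so not too small.

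**6. Standard error of the slope.** With n = 10, CV 10% and kappa SD 1, ordinary regression gives √[2.657 / (10 × 26 × 65.72)] = 0.0125, against a simulated sampling SD of 0.0006. The ordinary SE is about 20 times too large. The tiny sampling SD is itself a product of the leave-one-out scaling, not a sign of precision.

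**The case against.** The strongest reply is that the SAP is silent rather than wrong. It does not say that points are pooled or treated as independent, or that both trials enter, and it states no standard error or interval for this regression. That stands: a reader might infer that the planned error bars are wrong, but there are none to be wrong.

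A reader might also infer that the slope interval is too narrow, the usual result of ignoring clustering. Under the SAP's leave-one-out HR the reverse holds (step 6). A slope interval that is too narrow could arise if one fixed external HR were applied to everyone, but that is not the analysis the SAP describes.

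It can fairly be said that individual error is not lost altogether. Residual scatter carries it, and the SAP fits HR and kappa for each subject, so the spread can be computed. This limits the criticism to the slope as a summary. It does not remove it, because the only agreement analysis planned for Aim 1 concerns repeatability of HR and kappa, not error against the true angle.

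Finally, a reader might extend the clustering point to Aim 2, since the protocol (Clinical study) says "Each subject was tested three times with the app in quick succession". Those readings belong to the phoria comparison with the Modified Thorington test. The SAP's Aim 2 compares strabismus angle with the prism cover test, and no document says that comparison had three app readings per subject. The extension is not supported.

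**Conclusion.** The point holds in a limited form and should be acted on. If the accuracy regression is pooled, its slope is about 1 whatever the spread of HR between subjects, so it cannot answer the question the SAP sets for it. This part follows from the algebra and needs only common targets, a leave-one-out mean HR and the app estimate as response. The sizes (individual slope SD 0.06-0.11; 1.3-2.6 degrees at 13 degrees for a subject 2 SD out) depend on the assumed CV of 5-10% and, for the SD, on the assumed noise.

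The clustering part is conditional. A standard error for the mean difference that ignores subjects is about 3 times too small only if kappa is left in and varies by about 1 degree SD with both trials pooled. With no kappa variation it is not too small. The documents do not support a claim that any stated interval is wrong or that the slope interval is too narrow.

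**What to change.** Keep the leave-one-out HR, and state the unit of analysis, which trials enter and whether kappa is removed. Then report:

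- each subject's slope and mean error, or a mixed model with random intercept and random slope by subject;
- the between-subject SD of the slope and the error range it implies at the largest target angle;
- bias and limits of agreement for app minus true angle, by a method that allows for repeated measures;
- intervals from a bootstrap that resamples subjects and recomputes the leave-one-out HR each time.

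The pooled slope may stay as a description, with a note that it is near 1 by construction.

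This needs no new subjects or measurements. The SAP is dated August 1, 2019 and says it was produced during publication of the data, so the change is a re-analysis and a reporting clarification on existing data.

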#### BACKGROUND:

The goal of the proposed project is the development and evaluation of a novel mobile medical application for the detection and monitoring of strabismus (eye misalignment). The image analysis technology necessary to measure strabismus using the corneal reflection technique (Photographic Hirschberg Test) has been available for many decades (Brodie 1987), however it has never been deployed using a smart phone. A smart phone platform will eliminate barriers of cost (since the hardware is maintained and updated by the smart phone industry), leading to rapid widespread application and allowing the technology to finally reach its potential level of impact for children's' eve care in the detection and management of strabismus. Strabismus causes visual confusion and double vision which ultimately results in the brain suppressing vision from the deviated eye. In children this results in under-development (amblyopia) with permanent vision loss in the deviated eye if not detected and treated at a young age (Rowe, 2012). Strabismus in children is also associated with coordination problems such as postural instability (Lions et. al. 2013) and severe social disadvantages (Lukman et. al. 2011). Strabismus develops in an estimated 3-8% of children in the U.S. (Taylor et.al. 2011; Cotter et.al. 2009; Rowe 2012). The prototype smart phone app (Referred to here as the Mobile Eye Alignment App – MEAA), uses photographic analysis of the corneal reflection (Purkinjie image) generated by the smart phone camera flash. The corneal reflection method uses the displacement of the reflection from the center of the pupil in the deviated eye to calculate the amount of eye misalignment.

This measurement technique will be deployed for the proposed project using the hardware of the Samsung Galaxy, a popular phone with an Android operating system. Preliminary results suggest the app can measure differences in eye alignment of  $1.6^{\circ}$  (2.8 prism diopters). If successfully developed, the app has potential to be utilized to advance pediatric strabismus research by facilitating and reducing the cost of collecting enormous amounts of data from the general population and underserved or remote populations for epidemiologic studies and allowing researchers to capture eye alignment data much more frequently than is currently possible. Such a tool could better delineate the natural history of strabismus and perhaps help determine its causes.

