## AIM 2:

Evaluate the strabismus app accuracy and feasibility in a clinical environment. Participants with strabismus will be tested with both the app and clinical methods and analyzed for levels of agreement and test-retest repeatability, satisfaction with the app evaluation, impact on symptoms, and perceived value.

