## **OBJECTIVES**:

1) Using simulated strabismus, we will systematically evaluate changes to the prototype app. The app will be tested in various lighting conditions and in participants with various iris colorations, using this information to refine and eventually select the best algorithm.

2) Compare the app measurement with the following common clinical tests of eye alignment: the cover-test with prism neutralization, modified Thorington, or Von Graefe method to determine accuracy, test-retest variability, and robustness of the prototype (optimized in objective 1) to accurately measure strabismus.

3) Determine the best methods for tele-strabismus consultation and rapid delivery of prism treatment, develop a user interface, and determine the perceived value.

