## **HYPOTHESES**:

For strabismus ranging from 1 to 30 prism diopters (target range), the optimized version of the app will provide measurements which are not significantly different from the ground truth (simulated strabismus) or clinical tests of eye alignment.

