## **STUDY OUTCOMES**

## Primary outcome:

The primary outcome is a comparison between the app and the ground truth and between the app and clinical tests.

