Figure 2. Cover testing mode for dissociated measurements using the app. (Top row) Alternating cover–uncover test using the video-based cover test mode. This novel operational mode can be used for dissociated measurements. The examiner alternately covers the eyes (first two images on top row). The frame with both eyes uncovered (third image on the top row) is selected for automatic processing by the app for measurement of the eye deviation. (Bottom row) Eye movement trace after offline processing of the video of the alternate cover test shows the movements of the eyes after the cover is removed. Negative values show temporal deviation (outward), whereas positive values show nasal deviation (inward). There is a brief duration after removing the cover during which the deviation can be measured (highlighted by the oval gray zone). It should be noted that the eye movement trace in this figure was generated by processing the video recorded by the smartphone on a desktop computer using the same image processing software used in the app, but may be included as part of the app in the future. Permission to publish photograph was obtained via a signed consent to publish document.

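### SAP Aim 2 names only linear regression of app against CTPN; it omits the protocol's mean difference, and neither document gives a method for the spread of individual differences

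*SAP*

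**What the plan says.** **Protocol.** The Aim 2 section says that participants with strabismus will be measured by the app and by clinical methods and "analyzed for levels of agreement and test-retest repeatability". Objective 2 sets the app against clinical tests, CTPN among them, "to determine accuracy, test-retest variability, and robustness of the prototype". The primary outcome names no statistic: "The primary outcome is a comparison between the app and the ground truth and between the app and clinical tests". The first secondary outcome does name one: "Accuracy of the app quantified by calculating the mean difference between the app and simulated or measured strabismus".

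**SAP, Aim 2: Strabismus.** One analysis is named: "Linear regression analysis was used to compare the app measurements of strabismus angle with cover test with prism neutralization CTPN measurements". The rest of the section describes a correction of the CTPN values for the distance between the prism and the eye's centre of rotation.

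**SAP, Aim 1: Simulated Strabismus.** Here the SAP says what the slope and intercept stand for (the Hirschberg ratio and angle kappa). It uses a Bland-Altman plot for the test-retest repeatability of those two quantities. That is the only Bland-Altman analysis in either document, and it compares two app trials, not the app with CTPN.

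**The concern.** Agreement between two methods has two parts: the systematic difference, and how far individual pairs scatter around it. The protocol promises agreement and defines a statistic for the first part. The SAP section that should deliver both names a regression and does not say which of its outputs are reported, which variable is on x, whether angles are signed, or how the result is to be judged.

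The clinical comparison is half of the primary outcome, and the protocol leaves that outcome as an unspecified comparison, so the SAP is where the statistic has to be fixed. If only a slope and a goodness-of-fit figure are reported, an app with a sizeable constant bias looks the same as one with none. If the intercept is then read as the bias, it can suggest a bias that does not exist or hide one that does. In either case a clinician does not learn how far one patient's app reading may lie from CTPN.

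**Working it through.** The documents give no Aim 2 sample size, SD or result, so there is no plan figure to reproduce. The figures below are illustrations. Only the 1 to 30 PD range comes from the documents (protocol, Hypotheses). The uniform distribution, the error SDs, the biases and the slopes are assumed.

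**Angle distribution.** Unsigned angles uniform on 1 to 30 PD have mean 15.5 and variance 29²/12 = 70.08.

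**General relations**, for app = a + b·x + residual with SD s:
- mean difference = a + (b − 1)·mean(x)
- SD of differences = √[(b − 1)²·var(x) + s²]
- R² = b²·var(x) / [b²·var(x) + s²]
- 95% limits of agreement = mean difference ± 1.96 × SD of differences

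**1. A constant bias leaves slope and fit unchanged.** Take error-free CTPN, b = 1 and s = 2 PD. Then R² = 70.08/(70.08 + 4) = 0.946 whatever the bias.
- Bias 0: limits 0 ± 3.92, that is −3.9 to +3.9 PD.
- Bias 6 PD: limits 6 ± 3.92, that is +2.1 to +9.9 PD.

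Slope, R² and residual SD are the same in both cases. Only the intercept differs.

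**2. The intercept is not the bias when b ≠ 1 and mean(x) ≠ 0.** Take a = 0, b = 0.8, s = 1 PD.
- R² = 0.64 × 70.08/(0.64 × 70.08 + 1) = 0.978
- Mean difference = 0 − 0.2 × 15.5 = −3.1 PD
- SD of differences = √(0.04 × 70.08 + 1) = 1.95; limits −6.9 to +0.7 PD

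Fit is high and the intercept is 0, yet the app reads 3.1 PD low on average.

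**3. Error in CTPN produces the opposite mistake.** Take an unbiased app with noise SD 2 PD and put CTPN, with error SD e, on x. Then slope = 70.08/(70.08 + e²), intercept = 15.5 × (1 − slope), and SD of differences = √(4 + e²).

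| e (PD) | slope | intercept (PD) | mean difference (PD) | limits (PD) |
|---|---|---|---|---|
| 2 | 0.946 | 0.84 | 0 | ±5.5 |
| 3 | 0.886 | 1.76 | 0 | ±7.1 |
| 5 | 0.737 | 4.08 | 0 | ±10.6 |

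Check for e = 3:
- Mean difference: 1 − slope = 9/79.08 = 0.1138, so it is 1.764 − 0.1138 × 15.5 = 0.
- Spread: residual variance = 74.08 − 0.8862² × 79.08 = 11.98, so the SD of differences is √(0.1138² × 79.08 + 11.98) = 3.61, which equals √(4 + 9).

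**4. The sign convention changes the answer.** Suppose the app reads every angle 10% low with noise SD 2 PD, against error-free CTPN.
- Unsigned: bias −0.1 × 15.5 = −1.55 PD; SD √(0.01 × 70.08 + 4) = 2.17; limits −5.8 to +2.7 PD.
- Signed, split evenly between directions: mean 0, variance 70.08 + 15.5² = 310.33; bias 0; SD √(0.01 × 310.33 + 4) = 2.67; limits ±5.2 PD.

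In the evenly split signed case the intercepts in step 3 would also be 0.

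**The case against.** The strongest reply is that regression output can carry the missing information. This is correct. Bias follows from slope, intercept and the mean of x. When the slope is 1, intercept ± 1.96 × residual SD gives the limits directly, and a plot of the pairs would also show the spread. A reader might therefore infer that regression cannot reveal disagreement, or that agreement with CTPN cannot be known. The documents support neither. They support only that the SAP does not commit to reporting the outputs that would show it.

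Second, the protocol already defines the mean difference for measured strabismus, and the SAP does not withdraw it. This also stands in part: for bias the gap is a failure to carry the outcome forward, not its removal. Spread is absent from both documents.

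Third, the sizes above depend on assumed SDs, and at CTPN error SDs of 2 or 3 PD the spurious intercept is below 2 PD. That is fair. The algebra does not depend on those values, but the size does.

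Three further inferences should be resisted:
- The eye-movement trace in protocol Figure 2 is signed, but the caption says it was processed offline on a desktop computer. It does not show that the app readings compared with CTPN were signed.
- The distance correction of CTPN is stated in the SAP and is not a fault.
- The three app readings per subject in the protocol's Clinical study section belong to the phoria comparison with the Modified Thorington test. They do not show that repeat strabismus readings exist.

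**Conclusion.** The point holds in this form. The only comparison the SAP states for app against CTPN is a regression with unspecified outputs, the protocol's mean difference is not carried into it, and neither document gives a method for the spread of individual differences. The plan thus does not commit to answering the agreement question the protocol sets for Aim 2.

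The size in this trial cannot be computed. Under the assumptions shown, an unbiased app can have an intercept of 0.8 to 4.1 PD with limits of ±5.5 to ±10.6 PD, and an app 6 PD high can have the same slope and fit as an unbiased one. The textual finding does not rest on any of these values. It should be fixed, because it concerns the main clinical comparison and is cheap to close. It does not show that the app agrees poorly, or that the sponsor failed to look at agreement.

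**What to change.** Make the main Aim 2 agreement analysis the mean app-minus-CTPN difference with its confidence interval, together with the 95% limits of agreement and their confidence intervals. Use the distance-corrected CTPN values, state the sign convention, and check whether the differences vary with the size of the deviation.

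Keep the regression as supportive. State which variable is on x, and report slope and intercept with confidence intervals and the residual SD.

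Report test-retest repeatability of strabismus angle only if repeat readings were taken; otherwise state that it was not assessed.

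Label these analyses supplementary, since the SAP's own heading says it was prepared while the data were being published.

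The cost is low: the paired readings and corrected CTPN values exist, and no new data are needed. The downside is that the intervals may look less favourable than a regression fit, and the additions are post hoc and cannot restore prespecification.

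### The Aim 2 regression of app readings against CTPN makes no allowance for random CTPN error, so its slope may be a biased measure of the app's proportional error

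*SAP*

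**What the plan says.** The SAP section on Aim 2 gives one comparison of the two methods: "Linear regression analysis was used to compare the app measurements of strabismus angle with cover test with prism neutralization CTPN measurements". It does not name the estimator, say which measurement is the outcome, state whether eso- and exo-deviations carry opposite signs, or set a criterion for slope or intercept. CTPN receives one adjustment: "corrections were made to the recorded CTPN values during data processing to account for the finite distance" between prism and eye. That adjustment uses fixed constants, "assuming a population average value of 24 mm for axial length" together with a 10 mm back vertex distance.

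In Aim 1 the SAP fits its regression "by plotting the app measurement against the known angular deviation for each fixation point", so there the predictor is a set angle. Bland-Altman appears in the SAP only for Aim 1 test-retest, "in estimating the HR and κ using a Bland-Altman" plot.

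The protocol asks for more. Its Aim 2 says participants with strabismus will be "analyzed for levels of agreement and test-retest repeatability". Objective 2 is to "Compare the app measurement with the following common clinical tests of eye alignment" in order to establish accuracy, repeatability and robustness. Secondary outcome 1 defines accuracy as a mean difference from simulated or measured strabismus. The SAP's Aim 2 text carries over neither the mean difference nor an agreement analysis.

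**The concern.** Least squares treats the predictor as free of error. That is reasonable in Aim 1, where the target angles are set by geometry. In Aim 2 the natural predictor is a manual clinical measurement. A correction built on population constants changes its scale but removes none of its random error. Classical error in the predictor pulls the slope towards zero, and a larger sample does not cure this.

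The slope matters for this device. According to the protocol's Study Procedures, the app converts reflection displacement to prism diopters with a Hirschberg ratio taken from the range of published values. An unsuitable ratio would appear as proportional over- or under-reading, which is what a method-comparison slope is meant to show. An attenuated slope could make a well-calibrated app look as if it under-reads, or make one that over-reads look well calibrated.

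**Working it through.** The plan states no slope, error SD or sample size for Aim 2, so there is no figure to reproduce.

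**Inputs**
- Range of angles: the protocol's Hypotheses section, "For strabismus ranging from 1 to 30 prism diopters (target range"). A uniform distribution is assumed.
- CTPN random error SD, s: not in the documents; 2, 3 and 4 PD assumed.
- App random error SD: not given for Aim 2; 2 PD assumed where needed. It does not affect the expected slope of app on CTPN.
- Error model: CTPN = T + e and app = g·T + noise, with T the true angle, g the app's gain, and independent errors.

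**Formula.** The expected least-squares slope of app on CTPN is g·λ, with λ = Var(T) / (Var(T) + s²).

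**Spread of angles**
- Unsigned: Var(T) = 29²/12 = 70.08, SD 8.37 PD, mean 15.5 PD.
- Signed, with eso and exo balanced: Var(T) = 70.08 + 15.5² = 310.33, SD 17.62 PD, mean 0.

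**Results.** The slope column is for an accurate app (g = 1). The gap is (1 − λ)(30 − mean). The last column is the over-reading that gives an expected slope of exactly 1, which is 1/λ − 1.

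| Angles | s (PD) | Expected slope | Intercept (PD) | Fitted line low at 30 PD by (PD) | Over-reading with slope 1 |
|---|---|---|---|---|---|
| Unsigned | 2 | 0.946 | 0.84 | 0.78 | 5.7% |
| Unsigned | 3 | 0.886 | 1.76 | 1.65 | 12.8% |
| Unsigned | 4 | 0.814 | 2.88 | 2.70 | 22.8% |
| Signed | 2 | 0.987 | 0 | 0.38 | 1.3% |
| Signed | 3 | 0.972 | 0 | 0.85 | 2.9% |
| Signed | 4 | 0.951 | 0 | 1.47 | 5.2% |

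For example, unsigned with s = 3: 70.08 / (70.08 + 9) = 0.886. Simulation with 1,000,000 pairs per scenario agreed with the formula to about 0.002.

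**Sampling variation.** These are expected values. With unsigned angles, app error SD 2 PD and an assumed n of 30, an accurate app gave a slope below 1 in 81% of simulated samples at s = 2 and 94% at s = 3.

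**Axes reversed.** If CTPN is regressed on the app, app error attenuates the slope instead. For an accurate app with error SD 2 PD and unsigned angles, the expected slope is 70.08 / (70.08 + 4) = 0.946. With a noise-free app it is 1.

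**Does Deming regression help?** With unsigned angles, app error SD 2 PD and the correct error-variance ratio, simulated Deming slopes for an accurate app were 1.000 at s = 2 and 0.999 at s = 3. Apps with true gains of 1.057 and 1.128 were recovered at those values. The ratio matters. At s = 4 the true CTPN:app variance ratio is 16/4 = 4; assuming 0.5, 1 or 2 gives an accurate app slopes of 0.88, 0.92 and 0.96, and assuming 4 gives 1.00.

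**The case against.** The strongest objection is that the attenuation is conditional and its size unknown. The SAP names neither estimator nor axes for Aim 2, and app-on-CTPN is inferred from Aim 1. Error of Berkson type would not attenuate the slope, and positively correlated errors would lessen the effect: correlations of 0.3 to 0.6, with CTPN SD 3 and app SD 2 PD, move the unsigned slope from 0.886 to between 0.909 and 0.932. The protocol's eye-movement figure gives temporal and nasal deviations opposite signs, so a signed analysis is plausible, and then the effect is small. All of this stands. It limits the size and makes the point conditional, but nothing in the SAP removes the problem.

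A reader might infer that the whole Aim 2 accuracy conclusion rests on this slope. The documents do not support that, because the protocol defines accuracy as a mean difference, which slope attenuation does not affect. The safeguard is partial. With unsigned angles, the over-reading that the slope hides would appear as a mean difference of 0.88, 1.99 or 3.54 PD for s = 2, 3 or 4; with balanced signed angles it averages to zero.

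A reader might also infer that the regression could reject an accurate app. No document sets a slope or intercept criterion by which that could happen.

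Finally, the SAP says it was produced during publication of the data, so any change is a reanalysis. That is a fair caution about how to present it, not a reason to leave the slope uncorrected.

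**Conclusion.** The concern holds in conditional form. If Aim 2 uses least squares with the app as outcome and CTPN error is classical, the expected slope understates the app's gain. For CTPN error SDs of 2 to 4 PD the understatement is about 5% to 19% with unsigned angles and about 1% to 5% with signed, balanced angles, each uniform over the target range. The documents do not settle which case applies, because the error SD and the distribution of angles are both assumptions here.

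It would be tempting to set the 2.7 PD shortfall at 30 PD beside the 2.8 PD difference that the protocol's Background says the app can measure. That figure combines the largest error SD tabulated, unsigned angles and the end of the range, so it is not a typical effect. Nor does an accurate app always show a slope below 1; the statement concerns the expected slope. The Aim 1 regressions on known target angles are not affected.

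**What to change.** In the SAP's Aim 2 section:

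1. State the estimator, which measurement is on which axis, and whether eso- and exo-deviations are signed.
2. Report the protocol's mean difference, with limits of agreement, for app minus CTPN.
3. Base statements about proportional bias on Deming regression with bootstrap confidence intervals resampled by subject. Keep the least-squares line as descriptive.
4. Take the error variances from repeat app and CTPN readings in participants with strabismus where these exist. The protocol's Aim 2 calls for test-retest repeatability, but the three app repeats it describes belong to the phoria comparison with Modified Thorington and should not be assumed to serve here.
5. Where repeats are lacking, show results over a wide range of CTPN:app error-variance ratios, for example 0.5 to 4. Claim proportional agreement or bias only if the claim holds across that range. A range ending at 2 would miss the s = 3 and s = 4 scenarios above, whose ratios are 2.25 and 4 with app SD 2 PD.

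The cost is SAP wording and a short rerun on data already collected. The downsides are that the ratio may have to be assumed, the interval is somewhat wider, and the result must be labelled a reanalysis.
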